# SYNOPSIS

Study Title	Randomized Trial Evaluating Effectiveness of neoClose ® Abdominal Closure Device versus CarterThomason ® Needle Passer
Trial Design	A randomized trial intended to compare neoClose ® abdominal closure versus standard Carter- Thomason ® closure in a bariatric surgery gastric bypass and sleeve gastrectomy population. The primary objective of the study is to compare the technical effectiveness of the devices. A secondary outcome will be analysis of pain scores associated with the distinct closures.
	The study will be by a group of 6 Bariatric / General Surgeons at a high volume academic institution. Patients will be randomized upon induction of anesthesia and blinded to the closure technique performed. Video analysis of technical effectiveness will be performed as well as clinic follow up at 1 week ,6 weeks and 1 year after the procedure to assess pain scores. In addition, an abdominal ultrasound will be completed at 6 weeks and 1 year to evaluate the incidence of port site hernia.
Procedure	Both devices will be used to close 12 mm camera and stapler port sites upon completion of a robotic assisted laparoscopic gastric bypass and sleeve gastrectomy. The procedure requires a 12 mm port be placed in the midline approximately 3 cm cephalad to the umbilicus and a second in the right mid abdomen. Port sites will be closed as defined as the inability to palpate a fascial defect .

Study Population	Adults aged 18-70 years with BMI > 35 that have completed a multimodality bariatric workup (EGD, nutrition evaluation and psychological evaluation) and selected to have an elective gastric bypass and sleeve gastrectomy. Subjects who fail to complete extensive pre-operative work up including endoscopic surveillance, nutrition visit, psychological clearance will be excluded from the study. A pregnancy test will be done on female subjects as part of Standard of care. There will be 35 patients per group. A power analysis was completed using the data derived from our preclinical porcine study using primary endpoint of time (32 seconds for Carter- Thomason® and 18.5 seconds for neoClose®). The alpha utilized was 0.05. A total of 70 patients will be screened for the study.
Assessments	
 
The study will allow for the evaluation of technical effectiveness and analysis of pain scoring:
 
Technical Effectiveness 
 
Number of sutures required to complete closure.
 
Time required to complete closure.
 
Depth of needle penetration to complete closure.
 
Evaluate for surgical site occurrences immediately post op as well as at 1 ,6 weeks and 1 year after closure procdure.
 
Evaluation for port site hernia at 6 weeks with abdominal ultrasound.
 
 
 
Pain Evaluation 
 
Visual analog pain scale will be used to assess pain at both port sites.
 
Amount of intravenous narcotics required during hospitalization.
 
Hospital stay duration.
 
 
 
The study will allow for assessment of pain scores during hospitalization and at follow up visits approximately 1 week ,6 weeks and 1 year.
 

Data Collection	During the procedure, an independent examiner will record the amount of time and number of suture passes to obtain port site closure. In addition, an independent review of video from each procedure will be completed to record the time and depth of needle exposure. Patients will fill out pain analog scores

	during hospital stay and follow up visits. Care givers on the floor and in clinic will
	be blinded to the closure technique.
	Hospital records will be reviewed to record narcotic requirements.

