#### **B. STUDY DESIGN AND PROCEDURE**

#### **Patient Allocation**

This is a randomized study consisting of 35 patients. This site will be the only site across the US doing the study. On the morning of the procedure, qualified subjects who were consented for the study will be randomized to fascial closure with either the neoClose® device or a Carter-

Thomason® suture passer. The floor team and the subjects will be blinded to the closure technique.

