#### **Data Analysis**

Data will be analyzed using a simple T test within the Excel program as there will be only two groups with a single variable between them. Post Hoc analysis will not be required as with ANOVA secondary to the lack of a third group.

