# **E. STUDY GUIDELINES**

# **Patient Population**

Subjects will be patients aged 18-70 that have been evaluated by a multimodality team including a surgeon, nutritionist, and psychiatrist then scheduled for a robotic assisted gastric bypass and

sleeve gastrectomy. Once surgery has been approved patient will be considered for the study if they have no prior history of midline laparotomy and are having a de novo gastric operation.

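### The plan screens 70 patients to fill two groups of 35: either *screened* should read *randomized*, or the stated size has no margin for ineligible or declining patients (minor)

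*Combined protocol and SAP*

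**What the plan says.** The Study Population entry of the Synopsis gives the group size as "There will be 35 patients per group" and, a few sentences later, the number to be screened: "A total of 70 patients will be screened for the study". The Data Analysis section confirms two arms: "there will be only two groups with a single variable between them".

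Not everyone screened is randomized. Under Patient Allocation, "qualified subjects who were consented for the study will be randomized to fascial closure". The same Synopsis entry sets age and BMI limits and an exclusion: "Subjects who fail to complete extensive pre-operative work up including endoscopic surveillance, nutrition visit, psychological clearance will be excluded from the study". Under Patient Population, a patient is considered once surgery has been approved, and only "if they have no prior history of midline laparotomy and are having a de novo gastric operation".

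Patient Allocation also gives a different total: "This is a randomized study consisting of 35 patients".

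The documents contain no screen-failure rate, no rule for replacing patients lost before randomization, and no statement on whether screening may go beyond 70.

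**The concern.** The number to be screened equals the number that must be randomized. A plan with eligibility conditions and a consent step normally screens more patients than it randomizes. This one has both and shows no difference between the two counts.

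What is at stake is whether the plan delivers the group size it states next to its power analysis. If the sentence is a slip of wording, a reader is misinformed about what 70 counts. If it is meant literally, the randomized total falls below 70 as soon as one screened patient is ineligible or declines.

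**Working it through.** **Inputs from the documents**
- Group size 35, two groups (Synopsis; Data Analysis).
- Number screened 70 (Synopsis).
- Alpha 0.05, sidedness not stated; closure time 32 s versus 18.5 s (Synopsis).
- Standard deviation, target power and screen-failure rate: not given.

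**Step 1. Head count.** Required: 2 x 35 = 70. Screened: 70. Margin: 70 - 70 = 0. One failure leaves at most 69.

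**Step 2. Can the 35 per group be reproduced?** No. The difference is 32 - 18.5 = 13.5 s, but a standard deviation and a target power are also needed. Solving the usual two-sample formula backwards, SD = 13.5 / [(1.96 + z_power) x sqrt(2/35)], two-sided, gives about 20.2 s for 80% power and 17.4 s for 90%. Neither value appears in the documents, so the stated size is taken as given.

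**Step 3. Shortfall for an assumed failure rate f** (ineligibility and refusal together):
- expected number randomized = 70 x (1 - f)
- standard error relative to 70 randomized = sqrt(70 / number randomized)
- number to screen to randomize 70 = 70 / (1 - f), rounded up

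| Assumed f | Randomized from 70 | Standard error ratio | Screen to reach 70 |
|---|---|---|---|
| 5% | 66.5 | sqrt(70/66.5) = 1.026 | 74 |
| 10% | 63.0 | sqrt(70/63) = 1.054 | 78 |
| 20% | 56.0 | sqrt(70/56) = 1.118 | 88 |

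**Step 4. Chance that nobody fails:** (1 - f)^70. This is 0.98^70 = 24% at 2%, 0.95^70 = 2.8% at 5% and 0.90^70 = 0.06% at 10%. These figures show only that some shortfall is likely under a literal reading. They do not show that it is large.

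**Step 5. Power, for illustration only.** Suppose 35 per group gave exactly 80% power, two-sided. The standard deviation then cancels, and power = Phi[(1.96 + 0.842) x sqrt(1 - f) - 1.96]. The results are 78.0%, 75.7% and 70.7% at f = 5%, 10% and 20%. Starting from 90% (1.282 in place of 0.842), they are 88.5%, 86.8% and 82.6%. Both starting values are assumptions.

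**The case against.** The strongest reply is that nothing is wrong with the numbers. Since 70 is exactly twice 35, the last sentence probably restates total enrolment with a loose verb. That is the likelier reading. It explains the sentence but leaves it inaccurate, because the plan elsewhere separates being considered for the study from being randomized.

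Second, a reader might infer that screening must stop at 70. The documents do not say so: the sentence names no maximum and gives no stopping instruction. Equally, they give no rule for continuing, so the point is left open.

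Third, most failures of the work-up or BMI conditions should occur before a patient reaches the study, because Patient Population considers patients only after surgery is approved. This is largely right and argues for a low failure rate. The Synopsis still lists an incomplete work-up as an exclusion, so that source is not closed entirely. Prior midline laparotomy, a non-de novo operation and refusal of consent clearly remain. The documents do not say whether a patient who declines counts as screened.

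Fourth, if the total of 35 in Patient Allocation were right, 70 screened would tolerate a 50% failure rate (35/70) and the problem would vanish. The point therefore depends on the Synopsis figure. That is the reasonable one to use, since it is given per group and stands beside the power analysis, but the two statements must be reconciled together.

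**Conclusion.** The inconsistency is real and minor. The Synopsis either uses the wrong word for the 70 patients or plans a screening number that leaves no room for anyone who is ineligible or declines. This conclusion takes 35 per group as the intended size.

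The size of the effect rests on failure rates that the documents do not give. At an assumed 5% or 10% the standard error rises by about 3% or 5%; it takes 20% to reach 12%.

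A reader might go further and infer that the trial will be underpowered. The documents do not support that. Without a standard deviation or a target power, it cannot be determined whether 33 or 31 per group would be too few, and the power figures above only illustrate assumed starting points.

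**What to change.** Replace the screening sentence in the Synopsis with: *A total of 70 patients will be randomized, 35 per group; screening continues until this number is reached, and patients who fail screening or withdraw before randomization are replaced.* At the same time, correct the total of 35 under Patient Allocation so that all sample-size statements agree.

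The cost is two edited sentences and a slightly longer screening period at one site that describes itself as high volume. The number randomized does not rise above the 35 per group already stated.

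If 70 screened is a genuine limit, the group size would have to be restated as the number expected from it. That needs a screen-failure rate, which the sponsor would have to supply.

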#### A. RATIONALE

Laparoscopic surgery requires the utilization of multiple ports with varying diameters. In the bariatric population, gastric bypass and sleeve gastrectomy requires 12 mm port placement for camera and stapler insertion. Many surgeons favor closure of the fascial defect in order to decrease the risk of hernia occurrence. Various type of port closure is available. The most popular closure device is the Carter-Thomason® needle. This device has inherent limitations:

(1) Insertion of the needle is associated with injury to the viscera and blood vessels.

(2) The width of the suture placed using the Carter-Thomason® needle can lead to compression of peritoneum and entrapment of underlying nerves, causing post-operative port site pain.

(3) Placement of the suture is challenging in the obese patient. 

Very few studies have been completed to compare novel devices to the Carter- Thomason® with equivocal data.  $^{(2)(3)}$ 

Current practice requires fascial closure with a suture passing needle which passes the suture material through some amount of subcutaneous tissue, muscle, and fascia. This technique is often associated with elevated levels of discomfort which can remain weeks after the operation is complete. In addition, the technique of port site closure can be difficult to learn leading to prolonged times potential needle exposure to underlying viscera as well as times for port site closure.

The development of a novel closure device which relies upon the guided deployment of suture / fasteners could help improve the learning curve associated with port site closure. In addition, such a technique that would not require passage of suture material through adjacent muscle and isolated the posterior fascia could lead to an improvement in patient satisfaction secondary to a decrease in pain.

The neoClose ® device is an abdominal closure device that has been approved by the FDA in 2013 (510K) to use as such. The study aims to add to the existing knowledge about these kinds of devices and also to evaluate the effectiveness of the neoClose® device compared to the Carter-Thomason® device. Moreover, surveys will also be administered to patients using the Visual Analog Scale of pain to establish pain scores associated with individual closures.

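### BMI is known for every patient and obesity is named as one source of difficult suture placement, yet BMI is neither recorded nor adjusted for: a cheap, modest gain in precision is left unused

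*Combined protocol and SAP*

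**What the plan says.** - **Combined protocol and SAP, A. Rationale.** The third of three listed limitations of the Carter-Thomason needle is "Placement of the suture is challenging in the obese patient". The same section also says that port closure can be hard to learn, and links that to longer closure and needle-exposure times.
- **Synopsis, Study Population.** Eligible patients are "Adults aged 18-70 years with BMI > 35". No upper BMI limit is given. The sample is 35 per group, 70 in all.
- **Section B, Patient Allocation.** Patients are randomized to one device or the other. No stratification by BMI is mentioned. (This section gives 35 patients for the whole study; the working below uses the Synopsis figure of 35 per group.)
- **Section B, Data Analysis.** "Data will be analyzed using a simple T test within the Excel program", on the ground that "there will be only two groups with a single variable between them". No covariate is named.
- **Section B, Data Collection, and Appendix 1.** BMI is not among the items to be collected and is on neither form. The MRN is to be deleted once the data are analyzed.
- **Section D, Primary Outcome Measure.** Closure time, time of the needle in the abdomen and needle depth are all among the primary measures.

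**The concern.** The reason given for the t test is that device is the only variable between the groups. Randomization makes device the only systematic difference between them, but it does not make device the only source of variation within them. The protocol names a patient characteristic that makes placement harder, and its value is available before randomization. If closure time, needle time or needle depth varies with BMI among these patients, the t test counts that variation as noise, and a chance difference in BMI between the arms goes unadjusted.

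What is at stake is the width of the confidence interval for the device effect, and the ease of answering a reader who notices unequal BMI in the two arms. The timing also matters: once the MRN is deleted, BMI may no longer be retrievable from the chart, and an adjustment chosen after the data are seen carries less weight than a prespecified one.

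**Working it through.** **1. The plan's own figure.** The sample size rests on mean times of 32 s and 18.5 s from a porcine study, a difference of 13.5 s, and "The alpha utilized was 0.05". No SD or power is stated, so 35 per group cannot be reproduced. Solving backwards (two-sided alpha assumed, normal approximation):

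SD = 13.5 × √(35/2) / (1.960 + z_power)

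- 80% power: 13.5 × 4.183 / (1.960 + 0.842) = 20.2 s
- 90% power: 13.5 × 4.183 / (1.960 + 1.282) = 17.4 s

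Either could have been intended. The rest assumes 80%.

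**2. Unadjusted baseline.** With the noncentral t distribution, 35 per group and 68 degrees of freedom, a standardized difference of 0.679 gives 80.0% power. Its noncentrality is 0.679 × √(35/2) = 2.840. One time value per patient is assumed.

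**3. Effect of adjusting.** Let r be the within-arm correlation of BMI with closure time. The documents give no value, so a range is shown.

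- Adjustment multiplies the residual variance by (1 − r²).
- Estimating the BMI slope costs one degree of freedom (67 remain). With 70 patients and a normally distributed covariate, it also inflates the variance on average by 1 + 1/66 = 67/66.
- Net variance factor: f = (1 − r²) × 67/66.
- Equivalent n per arm: 35/f. Noncentrality: 2.840/√f.

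| Assumed r | 1 − r² | f | Equivalent n per arm | Power |
|---|---|---|---|---|
| 0 | 1.00 | 1.015 | 34.5 | 79.3% |
| 0.1 | 0.99 | 1.005 | 34.8 | 79.7% |
| 0.2 | 0.96 | 0.975 | 35.9 | 80.9% |
| 0.3 | 0.91 | 0.924 | 37.9 | 83.0% |
| 0.4 | 0.84 | 0.853 | 41.0 | 85.8% |
| 0.5 | 0.75 | 0.761 | 46.0 | 89.4% |

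The variance breaks even where 1 − r² = 66/67, that is r = √(1/67) = 0.12. If only the degree of freedom is charged and not the average inflation, power is 81.5%, 83.5%, 86.3% and 89.8% at r = 0.2 to 0.5. The picture is the same, slightly more favourable.

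**4. Chance imbalance.** The difference in mean BMI between arms has SD √(2/35) = 0.239 of a BMI SD. At r = 0.3, an imbalance of that size moves the time difference by 0.3 × 0.239 = 0.072 of the SD of closure time. With the SD implied by step 2 (13.5/0.679 = 19.9 s), that is about 1.4 s against a planned difference of 13.5 s. This is not an extra penalty: averaged over randomizations, it is already part of the t test's standard error.

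**The case against.** The strongest reply is that nothing is invalid. An unadjusted comparison in a randomized trial is legitimate, and covariate adjustment is an optional efficiency gain. That stands.

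Three stronger readings are tempting, and the documents support none of them.

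- *That the protocol treats obesity as the cause of difficult closure.* It is one of three limitations listed for one device. The Rationale also cites difficulty of learning, and that is the statement it ties to longer times. The line on obesity mentions neither time nor depth.
- *That BMI is a known source of variation here, or the strongest predictor.* No section quantifies a relation between BMI and closure time. Every patient exceeds BMI 35, so the contrast between obese and non-obese patients is removed by eligibility. How far time varies with BMI above 35 is unstated. The absence of a ceiling permits a wide range but does not show one.
- *That ignoring BMI biases the device comparison.* Randomization rules this out.

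It is also fair to say that six surgeons and two operations may matter as much as BMI, and that the missing SD and power are a larger gap. Both are true, but neither is a reason to leave BMI unrecorded. Finally, because the Rationale attributes the problem to the comparator needle, the device effect might itself change with BMI. A model with a single device term does not test that; it estimates an average effect over the patients enrolled, which is what the t test also targets.

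**Conclusion.** The point holds as a low-cost precision improvement. The plan names obesity as one source of difficulty, has BMI available for every patient, and neither records nor uses it. The unadjusted test remains valid.

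From an assumed 80% power, the gain is about 1 point at r = 0.2, 3 at 0.3, 6 at 0.4 and 9 at 0.5. It is slightly negative, by less than 1 point, at r = 0.1 or below. A worthwhile gain therefore needs r of about 0.3 or more, and the documents do not say whether r is that large. The figures also assume 35 per group, two-sided alpha of 0.05, one value per patient and a linear BMI effect. The case for the change rests on the small worst-case loss and on the risk that BMI cannot be recovered later, not on a demonstrated BMI effect.

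**What to change.** 1. Add BMI at surgery to the operative data form in Appendix 1 and to the Data Collection list. Copy it from the chart before the MRN is deleted.
2. In Data Analysis, prespecify a linear model for closure time, needle time and needle depth, with device and continuous BMI as terms. Report the device coefficient with its 95% CI.
3. Keep the unadjusted t test as a sensitivity analysis.
4. Describe the expected gain as modest and dependent on an unknown correlation.

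The cost is one chart field, a sentence or two of analysis text, a regression in place of the t-test function, and one degree of freedom. If BMI proves unrelated to these outcomes, the loss is under 1 point of power. No additional patients are needed.

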#### **B. STUDY DESIGN AND PROCEDURE**

#### **Patient Allocation**

This is a randomized study consisting of 35 patients. This site will be the only site across the US doing the study. On the morning of the procedure, qualified subjects who were consented for the study will be randomized to fascial closure with either the neoClose® device or a Carter-

Thomason® suture passer. The floor team and the subjects will be blinded to the closure technique.

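### The design section sizes the trial at 35 patients and the synopsis at 35 per group, and the power statement cannot show which is meant

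*Combined protocol and SAP*

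**What the plan says.** Section B of the protocol, under Patient Allocation, gives the size of the whole trial: "This is a randomized study consisting of 35 patients".

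The Synopsis, under Study Population, says "There will be 35 patients per group". The Data Analysis section confirms that "there will be only two groups with a single variable between them", so the Synopsis figure means 70 patients.

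The Synopsis places its size beside a power statement: "A power analysis was completed using the data derived from our preclinical porcine study using primary endpoint of time". It gives mean times of 32 seconds for the Carter-Thomason device and 18.5 seconds for neoClose, and adds "The alpha utilized was 0.05". It then says "A total of 70 patients will be screened for the study".

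No other section states a sample size, and none gives an SD, a target power, the sidedness of the test or a dropout allowance.

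**The concern.** The number to randomize decides when enrolment ends and whether the trial can be reported as complete. Here two current sections differ by a factor of two. Stopping at 35 patients would comply with Patient Allocation and breach the Synopsis; stopping at 70 would do the reverse. The outlying number stands in the section that describes randomization, where trial staff are likely to look for it.

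A power calculation would normally settle which number was meant. This one cannot, because it omits the SD and the power. If the trial closed at the smaller size, the comparison of closure times would be less precise, and over a range of plausible SDs it would fall short of 80% power when the larger size would not.

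**Working it through.** **Inputs from the documents.** Total of 35 (Patient Allocation); 35 per group (Synopsis); two groups (Data Analysis); mean times 32 s and 18.5 s, and alpha 0.05 (Synopsis).

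**Inputs assumed.** Two-sided test (one-sided also tried), equal SD in both groups, one closure time per patient, and a range of SDs. A total of 35 is taken as 17 v 18.

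**Step 1: the two sizes.** 2 × 35 = 70, against 35. The gap is 35 patients, too large to be rounding.

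**Step 2: can the plan's figure be reproduced?** The difference is 32 − 18.5 = 13.5 s. In the normal approximation, n per group = 2 × SD² × (z for alpha + z for power)² / 13.5². With SD and power both unknown, this has no single answer. Solved backwards at two-sided 0.05, 35 per group corresponds to an SD of 20.16 s at 80% power, 17.42 s at 90% and 15.67 s at 95%. At 17.5 per group the SDs are 14.25, 12.32 and 11.08 s. Either size could have come from some SD, so the calculation does not identify the intended one.

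**Step 3: precision, for any SD.** The 95% CI half-width for the difference in means is t × SD × √(1/n₁ + 1/n₂).

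- 35 v 35 (68 df): 1.9955 × √(2/35) = 0.477 SD
- 17 v 18 (33 df): 2.0345 × √(1/17 + 1/18) = 0.688 SD
- Ratio: 0.688 / 0.477 = 1.44

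**Step 4: power, for assumed SDs.** Noncentral t, difference 13.5 s, two-sided 0.05:

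| Assumed SD (s) | 35 per group | 35 in total |
|---|---|---|
| 10 | >99% | 97% |
| 12 | >99% | 90% |
| 15 | 96% | 73% |
| 20 | 79% | 49% |
| 25 | 61% | 34% |
| 30 | 46% | 25% |

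**Step 5: where the conflict matters for 80% power.** With 35 per group, power is at least 80% if the SD is at most 19.87 s; with 35 in total, if it is at most 13.83 s. Between these limits the choice of size decides whether 80% is reached. Below them both sizes reach it, and above them neither does. At an SD of 19.87 s, 35 in total has about 50% power; at 13.83 s, 35 per group has about 98%. For a one-sided test the limits are 22.49 s and 15.72 s.

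**Step 6: the number screened.** Seventy screened gives 35 per group only if nobody is lost before randomization. Patient Population restricts entry: "patient will be considered for the study if they have no prior history of midline laparotomy and are having a de novo gastric operation". Patient Allocation adds consent: "qualified subjects who were consented for the study will be randomized to fascial closure". The documents do not say whether these steps come before or after screening, so this is a lesser wording point.

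**The case against.** The strongest reply is that this is a slip. The Synopsis is consistent with itself, since 35 per group and a total of 70 agree, and it is the only place that ties a size to a power calculation. Patient Allocation is a lone outlier that happens to equal the per-group number, so it has probably lost the words *per group*. On that reading the correction is a few words. This is fair, and it makes 70 the likelier intention. It does not settle the matter, because the only total given for the randomized study is 35 and the 70 is described as screened.

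The loss of power is also conditional. It changes whether 80% is reached only for SDs of about 13.8 to 19.9 s, and nothing in the documents places the SD there. SDs of 20 s or more would exceed the neoClose mean of 18.5 s, which is a lot for a time that cannot be negative, so those rows should not be read as likely. That stands, and it limits the weight of the power figures.

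Finally, two ports are closed in each patient and sutures are recorded by port, so the unit of analysis may not be one time per patient. In that case the SD limits would carry a different meaning; the ratio of 1.44 would be largely unaffected.

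**Conclusion.** The concern holds. The two stated sizes, 35 and 2 × 35 = 70, contradict each other, and nothing else in the documents resolves it. This needs no assumption, and it is what makes the point one that must be fixed.

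The cost of closing at the smaller size is a confidence interval about 44% wider, whatever the SD, given equal SDs and one time per patient. The effect on power depends on an SD that is not given. Neither size is shown to be inadequate: 35 per group can be neither verified nor refuted from the inputs stated. The missing SD and sidedness would be a reporting gap if they stood alone; here they matter because they leave the reader no means of telling which size was meant.

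**What to change.** The sponsor should confirm the intended number to randomize and make Patient Allocation and the Synopsis agree.

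- **If 35 per group is intended:** Patient Allocation should give 70 randomized patients, 35 per group, and the Synopsis should say that 70 will be randomized rather than screened.
- **If 35 in total is intended:** the Synopsis should be corrected, and the power stated for that size.
- **In either case:** add to the power statement the SD used, whether the test is one- or two-sided, whether the closure time is per patient or per port, and the power that the confirmed size has at that SD.

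If 35 per group is the plan, the cost is wording only. If 35 in total was meant, the trial is openly half the size given in the Synopsis, and its power has to be justified at that size.
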